Testing Adaptive Interventions to Improve Physical Activity for Sedentary Women

3/21/2018

NCT Number (not available yet)

Testing Adaptive Interventions to Improve Physical Activity for Sedentary Women

Statistical Analysis Plan

Under the direction of [name], SAS (v9.3) and R will be used for statistical analysis. Because multiple outcomes are being evaluated in the primary aim, a two-tailed .01 significance level will be used for the statistical tests of these hypotheses. Secondary and exploratory aims will employ a standard two-tailed significance level of .05 for all statistical tests. All analyses will be performed on an intent-to-treat basis. A one-way analysis of variance will be conducted to look for potential diffusion effects. If significant differences are found, the estimated mean levels of diffusion will be used as weights in the efficacy analyses and cost analysis. Hypothesis testing will address four study aims.

Aim 1. Aim 1 is to compare the two augmented treatments used for non-responders, personal calls and group meetings, in improving physical activity and cardiovascular health after 35 and 50 weeks.

Hypothesis: Group meetings will be more effective than personal calls in improving physical activity and cardiovascular health after 34 and 50 weeks, among non-responders to the initial treatment.

This hypothesis will be tested using a multilevel analysis with time nested within participant (i.e., non-responders only). The hypothesis of the study is that the non-responders who receive group meetings will demonstrate greater improvement in physical activity (self-report life-style and occupational physical activity: minutes of moderate/vigorous physical activity/weeks; device: number of steps/day, minutes of moderate/vigorous physical activity/ week) compared to those who receive personal calls.

Aim 2a. Aim 2a is to compare enhanced physical activity monitor with and without text messaging for improving the level of physical activity from baseline to 8 weeks. These analyses will parallel those used for Aim 1, but consider only two time points (baseline and 8 weeks) and include all participants.

Hypothesis: Participants who receive enhanced physical activity monitor+text messaging as compared to those who receive enhanced physical activity monitor alone will show greater improvement on physical activity at the end of 8 weeks.

Aim 2b. Aim 2b is to compare the four adaptive interventions in improving physical activity and cardiovascular health from baseline to 8, 34, and 50 weeks. The analysis is parallel to that described in Aim 1, except that the participants are not assigned to treatment based on simple randomization. Instead, they are screened on the basis of response status, and, once it has been ascertained that they did not respond to the initial treatment, they are randomly assigned to a treatment condition. Due to this design, the contrasts used to estimate the efficacy of these effects are nonorthogonal. The weights associated with the four interventions are then scored as a 4 for non-responder subgroups and 2 for responder subgroups. This is because responder subgroups are used twice in the design matrix (e.g., subgroup A is used in adaptive interventions 1 and 2; Figures 2 and 3). The estimation of these models is then based on a weighted multilevel linear regression model that has terms for change over time, the initial treatment, the augmented treatment, the interaction between the two treatments, and the effects of baseline and time-varying characteristics. The critical effect in this model is the time-by-adaptive-intervention interaction term. The null hypothesis is that there will be no interaction effect at all, while the alternative hypothesis is that adaptive intervention 4 (enhanced physical activity monitor+text messaging [initial] and enhanced physical activity monitor+text messaging with group meetings [augmented for non-responders]) will produce the largest improvement rates.

Aim 3. Aim 3 will identify mediators and moderators of the initial and augmented treatments on physical activity and cardiovascular health. Using analytic models parallel to those for Aims 1 and 2, we will first test impact on intervention targets (benefits, barriers, self-efficacy, social support).

Hypothesis: The intervention targets (benefits, barriers, self-efficacy, and social support) will mediate the effect of the initial and augmented treatments on physical activity (8, 34, and 50 weeks) and cardiovascular health (34 and 50 weeks).

Research Question: Do characteristics of participants (prior physical activity, demographics, BMI, depression) and their environment (walkability, crime) moderate the effects of the initial and augmented treatments on physical activity and cardiovascular health?

Although we will test the impact of each treatment on all potential intervention targets, we anticipate variation in impact by treatment (e.g., initial treatment is less likely to impact social support). For intervention targets that are significantly impacted by treatment condition, we will test whether they serve as mediators of intervention effects on physical activity and health status outcomes using methods described by MacKinnon. Moderation effects will be tested by adding moderator main effects and interactions of the moderators with condition and time. Significant moderator effects (i.e., significant moderator-by-time-by-treatment effects) will then be used to identify optimal decision rules for individual participants. The estimation of optimal decision rules will be achieved using a Q-Learning analysis, which is a modified regression analysis, adapted to address the SMART design. These optimal decision rules can then be cross-validated in future studies.

Aim 4. The cost-effectiveness analysis will be conducted from the societal perspective, including the program and participant costs. For the cost measurement, quantities of resources used and their associated prices will be collected for the program (either amounts paid or the value of the interventionist's time), and participant (i.e., the value of the participant's time to participate in the program). All costs will be valued in 2017 dollars. Program costs and participant costs will be calculated by summing their respective individual cost components, and these costs will be summed to calculate the total cost per participant.

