- All participants will be thanked for their time, and will schedule their appointment for the next study visit in 9-10 weeks

*Decision Point 1: Week 8*

- This aspect of protocol procedures does not entail an in-person visit with the research team
- At week 8, the research team will remotely determine if participants are deemed responders or non-responders to their initial treatment assignment based on their daily Fitbit step count synced to iCardia at UIC. A participant is considered a *Responder* to the initial treatment if she meets both of the following criteria for two of the three weeks during weeks 6-8 of the initial intervention phase:
  - 1) Have 3 or more valid days, defined as either 10 hours of wear time or steps greater than baseline average steps, and
  - 2) Average at least 600 steps above baseline steps for the valid days.
- If she is deemed a responder, she will continue her initial treatment (physical activity monitor or physical activity monitor+text messages)
- If she is deemed a non-responder, she will continue her initial treatment (physical activity monitor or physical activity monitor+text messages) and, in addition, be randomly assigned to receive either of the two augmented treatment conditions
  - Personal calls
  - Group meetings
    - See section **IX. Randomization** for further details on the randomization process

*Data Collection Weeks 9-10 and Augmented Treatment Appointment (D2)*

- Participants will be notified of whether they have been deemed a responder or non-responder to their initial treatment, and, if deemed a non-responder, will receive the results of their second randomization
- Because of changes related to COVID-19, participants will complete the D questionnaire online using a secure REDCap survey link
- D2 data collection will include the following:
  - Questionnaires:
    - Exercise Benefits/Barriers Scale (Revised for PA)
    - McAuley's Self-Efficacy for Overcoming Barriers to PA
    - Social Support and Exercise (Revised for PA)
    - International Physical Activity Questionnaire (IPAQ) long-form
    - Sedentary Behavior
    - Emotional Distress-Depression Short Form 8b
    - PROMIS Scale v 1.2
    - PROMIS Sleep Impact Short Form
    - Outcome Realizations
      - 11 items measuring realized change due to becoming more physically active

- Program Orientation Satisfaction Tool
  - 7 items measuring satisfaction with the Program Orientation Process
- Fitbit Satisfaction Tool

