  - Participants will be instructed to continue to wear their Fitbit monitor every day
    - Participants will only be wearing both monitors, the Actigraph and the Fitbit, simultaneously for one week during the prescribed Actigraph wear time

- Arrangements will be made by the research team to pick up participants' physical activity monitors one week later, or participants will have the option of returning their monitors to the College of Nursing using a secured metal drop-box on the outside of the main office door
- All participants will return to using only their Fitbit, and participants who received text messages or personal calls or group visits will be told that they have completed that part of the study
- Participants will be thanked for their time, and will schedule their final study visit, the Data Collection Weeks 51-52 (D4) appointment

*Final Data Collection Weeks 51-52 Appointment (D4)*

- Because of changes related to COVID-19, participants will complete the D3 questionnaire online using a secure REDCap survey link
- D4 data collection will include the following:
  - Questionnaires:
    - Exercise Benefits/Barriers Scale (Revised for PA)
    - McAuley's Self-Efficacy for Overcoming Barriers to PA
    - Social Support and Exercise (Revised for PA)
    - Outcome Realizations
    - International Physical Activity Questionnaire (IPAQ) long-form
    - Sedentary Behavior
    - Emotional Distress-Depression Short Form 8b
    - PROMIS Scale v 1.2
    - PROMIS Sleep Impact Short Form
    - Fitbit Satisfaction Tool
    - Diffusion Effects Measure
      - 2-part questionnaire that determines the degree to which participation in the program has influenced other Rush employees
    - For those in the Group Meetings Condition only:
      - Social Provisions Scale
    - Participant Satisfaction Tool
      - 12 items, five-point Likert Scale (Strongly agree to Strongly disagree) that asks questions related to satisfaction with the study.
  - Participants will be asked to come to the Physical Activity lab for a brief appointment to obtain:
    - Physical measures:
      - Three blood pressure readings, pulse, weight and waist circumference (a Physical Measures handout will be given to the participant that records these findings)
    - Fitness assessment
      - Step fitness test
- For the fourth time in the study, participants will be given an Actigraph to wear for one week
  - Participants will be instructed to continue to wear their Fitbit monitor every day

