## **XII. Hypotheses and Data Analysis**

Under the direction of [name], SAS (v9.3) and R will be used for statistical analysis. [name] is a methodological expert with a focus on developing innovating experimental designs, including the Sequential Multiple Assignment Randomized Trial (SMART) and will consult with [name] and members of the research team on use of the SMART design during the study. Because multiple outcomes are being evaluated in the primary aim, a two-tailed .01 significance level will be used for the statistical tests of these hypotheses. Secondary and exploratory aims will employ a standard two-tailed significance level of .05 for all statistical tests. All analyses will be performed on an intent-to-treat basis. A one-way analysis of variance will be conducted to look for potential diffusion effects. If significant differences are found, the estimated mean levels of diffusion will be used as weights in the efficacy analyses and cost analysis. Hypothesis testing will address four study aims.

**Aim 1.** Aim 1 is to compare the two augmented treatments used for non-responders, personal calls and group meetings, in improving physical activity and cardiovascular health after 35 and 50 weeks.

**Hypothesis:** Group meetings will be more effective than personal calls in improving physical activity and cardiovascular health after 34 and 50 weeks, among non-responders to the initial treatment.

This hypothesis will be tested using a multilevel analysis with time nested within participant (i.e., non-responders only). The hypothesis of the study is that the non-responders

who receive group meetings will demonstrate greater improvement in physical activity (self-report life-style and occupational physical activity: minutes of moderate/vigorous physical activity/weeks; device: number of steps/day, minutes of moderate/vigorous physical activity/week) compared to those who receive personal calls.

**Aim 2a.** Aim 2a is to compare enhanced physical activity monitor with and without text messaging for improving the level of physical activity from baseline to 8 weeks. These analyses will parallel those used for Aim 1, but consider only two time points (baseline and 8 weeks) and include all participants.

**Hypothesis:** Participants who receive enhanced physical activity monitor+text messaging as compared to those who receive enhanced physical activity monitor alone will show greater improvement on physical activity at the end of 8 weeks.

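### Mean diffusion should not become a weight in the efficacy analyses after a significant ANOVA: it is a post-randomisation quantity, not a probability or a precision

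*SAP*

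**What the plan says.** The opening paragraph of the SAP, repeated in Protocol section XII, sets a two-step rule. First: "A one-way analysis of variance will be conducted to look for potential diffusion effects". Then: "If significant differences are found, the estimated mean levels of diffusion will be used as weights in the efficacy analyses and cost analysis". The same paragraph also says: "All analyses will be performed on an intent-to-treat basis".

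Neither document states the ANOVA groups, its alpha or its instrument, whether more diffusion means more or less weight, how the weights are scaled, or how they combine with other weights. No rationale is given.

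The protocol contains one diffusion instrument, the Diffusion Effects Measure. It appears only in the D4 list (section IV, weeks 51-52) and is described as a "2-part questionnaire that determines the degree to which participation in the program has influenced other Rush employees". That the ANOVA would use it is an inference, but there is no other candidate.

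Two analyses that the rule would touch matter here. Aim 2a compares the initial treatments and is to "consider only two time points (baseline and 8 weeks) and include all participants". Aim 2b already carries weights of 4 for non-responders and 2 for responders. Protocol section XI randomises 1:1 at both stages, the second stage in non-responders only.

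**The concern.** A weight in an efficacy analysis needs a justification: it undoes unequal assignment or sampling probabilities, or it reflects precision. Mean diffusion does neither. It is observed after randomisation and describes what participants passed on to colleagues, not what they received from other arms. A significance test would decide whether it is used at all.

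If the rule is triggered, it bears on the primary aim (tested at .01), on the week-8 comparison and on the adaptive-intervention comparison. Depending on details left open, it would misstate standard errors, or change the mix of women behind each mean and so bias the comparison.

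**Working it through.** The documents give no diffusion values, gains or SDs. All ratios, gains, response rates and SDs below are assumptions. The formulas are weighted least squares (WLS) on a single change score.

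**1. The plan's own weights.** With 1:1 allocation at both stages, the inverse probability of a non-responder's path is 1/(0.5 × 0.5) = 4, and of a responder's 1/0.5 = 2. Both match the SAP. With response rate p, responders on one adaptive intervention are p/2 of the sample and non-responders (1-p)/4. Their weighted totals are 2 × p/2 = p and 4 × (1-p)/4 = 1-p, so the weighted responder share equals p. A further factor that differs by response status breaks this equality.

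**2. Timing.** Aim 2a ends at week 8. The questionnaire is listed at weeks 51-52, which is 43-44 weeks (about 10 months) later.

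**3. Weights constant within each compared arm.** Arm means do not change. The ratio of model-based to true variance is

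V = [(n1w1 + n2w2)/(n1 + n2)] × [1/(n1w1) + 1/(n2w2)] / [1/n1 + 1/n2].

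- Equal arms, weights k:1: V = (1+k)²/(4k). The SE factor √V is 1.0011, 1.0062, 1.0206 and 1.0607 at k = 1.1, 1.25, 1.5 and 2. At k = 2 the .01 test runs at 2{1 - Φ(2.576 × 1.0607)} = .0063. An assumed 80% power becomes 1 - Φ(2.576 × 1.0607 - 3.418) = 75%, where 3.418 = 2.576 + 0.842.
- Arms of 100 and 50, double weight on the smaller: V = (200/150) × 0.02/0.03 = 0.889, so the SE factor is 0.943 and .01 becomes .015. With 1:1 allocation, 2:1 arms are not expected. The case shows that the error can go either way, not its likely size.

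**4. Aim 1, weights differing over the four non-responder cells.** Assume equal cells, no initial-treatment term in the model, and weights of 1 (monitor, calls), 2 (monitor+text, calls), 2 (monitor, meetings) and 1 (monitor+text, meetings). The monitor+text share is 2/3 in the calls arm and 1/3 in the meetings arm. One third of any initial-treatment effect then enters the calls-versus-meetings contrast.

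**5. Aim 2a, weights differing by response status.** Let k be the non-responder/responder diffusion ratio and gR, gN the mean gains. Each arm mean becomes

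(p·gR + (1-p)·k·gN) / (p + (1-p)·k),

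which shifts whenever k differs from 1. The contrast moves when k or p differs between arms.

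- k = 0.5 in one arm and 1 in the other, p = 0.5, no treatment effect: the responder share in the first arm becomes 0.667. The spurious difference is 600 × 0.167 = 100 steps/day for a 600-step gap between responders and non-responders, or 1,500 × 0.167 = 250 for a 1,500-step gap. A simulation (156 per arm, SD 2,000, 5,000 runs) gave 103 and 247, with type I error .074 and .175 at nominal .05. Without diffusion weights it was .051 and .048.
- Common k, response 60% v 40%, gains 1,500/300: the true difference is 1,020 - 780 = 240. At k = 1.1 it becomes 239; at k = 2 it is 814 - 600 = 214.

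**6. Aim 2b, diffusion multiplied onto 4/2.** The 4/2 factors cancel against the allocation, so the formula in step 5 applies. With p = 0.5 and gains 1,500/300 it reduces to (1,500 + 300k)/(1 + k):

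| k | 0.5 | 1 | 1.1 | 1.25 | 1.5 | 2 |
|---|---|---|---|---|---|---|
| Mean gain, steps/day | 1,100 | 900 | 871 | 833 | 780 | 700 |

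Two adaptive interventions with the same start differ spuriously only if k differs between calls and meetings. At k = 2 v 1 the shift is 148-200 steps/day over 30-70% response, and 25-33 if the gains are 800/600. The sign depends on which arm has more diffusion.

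**The case against.** **The trigger may never fire.** The oath of confidentiality at baseline asks women not to discuss the programme at work, and text messages continue in both responders and non-responders, so the documents give no reason to expect a large diffusion ratio between them. This stands and limits the likelihood of harm. It does not make the rule valid once triggered.

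**The scope is read in.** The text refers to the efficacy analyses without naming aims, and no instrument is tied to the ANOVA. Both readings are inferences, but neither document offers another.

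**The figures are single-score illustrations.** This also stands. The plan is a weighted multilevel model. In calculations for a random-slope model with weights acting on the residual variance and assumed variance components, the 200-step shift (k = 2 v 1) fell to between about 57 and 149, and the 6% excess in the Aim 1 standard error to 3-4%. Weights acting on the likelihood gave 200 again. The size depends on how the weights enter.

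**Stronger readings that do not hold.**
- That Aim 1 could at worst become slightly conservative: steps 3 and 4 show otherwise.
- That women without D4 data would be lost: group means are used, so they could still receive a weight.
- That Aim 2b standard errors are wrong because responders count twice: the documents name no variance estimator, which is missing detail, not a demonstrated error. Nor does step 1 guarantee unbiased means from duplicated responders in every weighted random-slope model.

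**Conclusion.** The rule is wrong as written for efficacy. Mean diffusion has no role as an efficacy weight whatever the groups or scaling; only the consequences depend on those details. Constant weights within each compared arm leave estimates intact and distort model-based standard errors. Weights that vary within an arm or adaptive intervention bias estimates, by an amount proportional to the responder/non-responder gap in Aims 2a and 2b. At week 8 such a gap is built into the definition of response, which requires a woman to "Average at least 600 steps above baseline steps for the valid days".

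A reader might infer that the trial's efficacy results will be biased. The documents do not support that: it would need a significant ANOVA and weights that vary within arms, and every ratio and gain used here is hypothetical. The conclusion is confined to efficacy. Whether spillover belongs in a societal cost analysis is a separate question. It should be fixed because the rule reaches the primary aim and the correction is simple.

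**What to change.** In both the SAP and Protocol section XII, remove the efficacy analyses from the sentence ending "the estimated mean levels of diffusion will be used as weights in the efficacy analyses and cost analysis". Keep the 4/2 weights of Aim 2b unaltered, and report diffusion by arm descriptively. If spillover to co-workers matters for the societal cost analysis, define it there as a separate sensitivity analysis, stating the groups, the formula and its role.

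The cost is wording in two documents and no new data. The one downside is that spillover no longer enters the main cost analysis; it is covered only if that sensitivity analysis is defined.

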## Testing Adaptive Interventions to Improve Physical Activity for Sedentary Women Study Protocol

### I. Purpose & Overview

The purpose of this study is to determine the most effective adaptive intervention combining four efficacious treatments (enhanced physical activity monitor, motivational text messaging, motivational personal calls, group meetings) to increase physical activity (step counts per day, minutes moderate/vigorous physical activity/week) and improve cardiovascular health (aerobic fitness, body composition) among sedentary women. This study with 312 women aged 18 to 70 will also assess treatment effects on intervention targets (benefits, barriers, self-efficacy, and social support). The four adaptive interventions compared in this study consist of an initial treatment component (*physical activity monitor* or *physical activity monitor+text messaging*) followed by an augmented treatment component (personal calls or group meetings) for those who do not respond to the initial treatment component. For ease of management, the research team will limit the augmented treatments to only two of the four factorial combinations of personal calls and group meetings. The research team will focus on personal calls only (least expensive) and group meetings (current standard) and accept inherent limitations. It is well-established that without intervention physical activity remains unchanged.

The combination of the two initial treatment components and the two augmented treatment components delivered to non-responders yields four adaptive interventions that will be evaluated in this study:

1. Start with enhanced *physical activity monitor*, augment with motivational personal calls for non-responders, and continue enhanced *physical activity monitor* for responders;
2. Start with enhanced *physical activity monitor*, augment with motivational group meetings for non-responders, and continue enhanced *physical activity monitor* for responders;
3. Start with enhanced *physical activity monitor+text messaging*, augment with motivational personal calls for non-responders and continue enhanced *physical activity monitor+text messaging* for responders; and
4. Start with enhanced *physical activity monitor+text messaging* augment with motivational group meetings for non-responders and continue enhanced *physical activity monitor+text messaging* for responders.

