## **XI. Randomization**

At the conclusion of the baseline interview, participants will be randomized to one of two initial treatments (physical activity monitor, or physical activity monitor+text message) in a 1:1 fashion. The random allocation table will be integrated into the Baseline interview programmed in REDCap, allowing both participant and interviewer to be blind to initial treatment condition until the end of the consent process and baseline interview.

At the end of the 8-week initial treatment phase, non-responders (i.e., those with an average increases of <600 steps per day above baseline) will continue their initial treatment assignment (physical activity monitor, or physical activity monitor+text message) and be randomized to one of two augmented treatments (personal calls or group meetings) in a 1:1 fashion stratified by initial condition using a random allocation table integrated into the Access database. Research staff will be blind to augmented treatment assignment until responder status has been entered into the Access database at the Decision Point 1 Week 8 time point. After their Week 9-10 (D2) follow-up appointment and after they return their ActiGraph, the participant will be notified if they are receiving an augmented treatment.

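### Aim 2a does not say how the pre-randomisation baseline enters the model, and its natural reading is a change-score contrast that leaves precision unused

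*SAP*

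**What the plan says.** For Aim 2a the SAP says the analyses will "consider only two time points (baseline and 8 weeks) and include all participants". The text is the same in Protocol section XII: "These analyses will parallel those used for Aim 1, but consider only two time points (baseline and 8 weeks) and include all participants". The model it borrows from Aim 1 is described in one sentence: "This hypothesis will be tested using a multilevel analysis with time nested within participant (i.e., non-responders only". For Aims 1 and 2a there is no list of fixed effects, no covariance structure and no statement of how the baseline outcome is handled.

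Only Aim 2b, also described as parallel to Aim 1, lists terms. They include time, the initial treatment and unspecified baseline and time-varying characteristics. The effect of interest there is the interaction of time with adaptive intervention.

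Protocol section XI fixes the order of events: "At the conclusion of the baseline interview, participants will be randomized to one of two initial treatments". Section IV places the screening week with both monitors before that interview, so device and questionnaire baselines both precede allocation.

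**The concern.** A two-occasion model with treatment, time and treatment-by-time terms estimates each arm's baseline mean separately. With complete data the interaction is then the difference between arms in mean change. That treats the baseline difference as unknown, although randomisation makes its expected value zero. A model that uses this fact estimates the same effect with a smaller standard error in large samples, unless the slope of follow-up on baseline is 1.

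What is at stake is the power of the text-messaging comparison and the width of its confidence interval. The documents give no power calculation for the 312 women, so they show no spare precision.

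**Working it through.** **Inputs from the documents.** Sample size: "This study with 312 women aged 18 to 70 will also assess treatment effects on intervention targets". Allocation: "physical activity monitor, or physical activity monitor+text message) in a 1:1 fashion", so 312 / 2 = 156 per arm. Women averaging 7,500 or more steps per day are excluded (Protocol sections II and IV). Test level: the SAP says "Secondary and exploratory aims will employ a standard two-tailed significance level of .05 for all statistical tests", while for the primary aim "a two-tailed .01 significance level will be used for the statistical tests of these hypotheses". Aim 2a is not labelled as either; I take it as secondary, at 0.05. The variance ratios do not depend on this choice. There is no stated power, effect size, SD, correlation or dropout, so there is no figure of the plan's own to reproduce.

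**Step 1: what the natural reading estimates.** In three simulated complete data sets, the treatment-by-time coefficient equalled the difference in mean change to four decimals (0.2727, 0.2795 and 0.4224). With 8-week values missing, this identity is no longer exact.

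**Step 2: general formula.** Let s0 be the baseline SD, b the slope of the 8-week value on baseline, and V the residual variance of that regression. Up to a common factor:

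- adjusted variance = V
- change-score variance = V + (1 − b)² s0²
- ratio (adjusted / change) = V / [V + (1 − b)² s0²]

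The ratio never exceeds 1. It equals 1, meaning no gain, when b = 1.

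**Step 3: equal variances (assumption).** With correlation r, b = r and V = s²(1 − r²), so the ratio is (1 − r²) / [2(1 − r)] = (1 + r)/2. Effective n = 312 × ratio. If the change-score test has 80% power, the adjusted test has power Φ[(1.96 + 0.842)/√ratio − 1.96].

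| r | 2(1 − r) | 1 − r² | ratio | 312 × ratio | power |
|---|---|---|---|---|---|
| 0.3 | 1.40 | 0.91 | 0.65 | 203 | 94% |
| 0.5 | 1.00 | 0.75 | 0.75 | 234 | 90% |
| 0.7 | 0.60 | 0.51 | 0.85 | 265 | 86% |

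Simulation (20,000 trials per correlation) gave inverse ratios of 1.53, 1.33 and 1.18, against 1.54, 1.33 and 1.18 from the formula. Both estimators were unbiased. In one data set with r = 0.5, imposing a common baseline mean cut the standard error from 0.1063 to 0.0927.

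**Step 4: steps, with baseline cut at 7,500 (assumed distributions).** Take an untruncated mean of 6,500, SD 2,500 at both occasions and slope 0.6.

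- Standardised cut: (7,500 − 6,500)/2,500 = 0.4. Then λ = φ(0.4)/Φ(0.4) = 0.3683/0.6554 = 0.562.
- s0² = 2,500² × (1 − 0.4 × 0.562 − 0.562²) ≈ 2.87 million.
- V = 2,500² × (1 − 0.36) = 4.00 million.
- Ratio = 4.00 / (4.00 + 0.16 × 2.87) ≈ 0.90.

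Over means 5,500 to 8,000, SDs 2,000 to 3,000 and slopes 0.4 to 0.8, the ratio runs from about 0.79 to 0.97.

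**Step 5: covariance for the common-baseline model.** A random intercept forces equal variances at the two occasions. In the Step 4 example they are 2.87 and 0.36 × 2.87 + 4.00 = 5.03 million, with average 3.95. The covariance is 0.6 × 2.87 = 1.72, so the fitted correlation is 1.72/3.95 ≈ 0.436.

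- Variance the model reports: 3.95 × (1 − 0.436²) ≈ 3.20.
- True variance: 5.03 + 0.436² × 2.87 − 2 × 0.436 × 1.72 ≈ 4.08.
- Reported over true standard error: √(3.20/4.08) ≈ 0.89, or about 11% too small.

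Over the Step 4 grid the shortfall is about 5% to 18%, and a nominal 5% test rejects about 6% to 11% of the time under the null. An unstructured 2x2 covariance allows the two variances to differ and so removes this problem.

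**The case against.** The strongest reply is that the plan does not commit to free baseline means. A two-occasion multilevel model with a common baseline mean fits the Aim 2a wording. The only list of terms belongs to Aim 2b, and its undefined baseline characteristics might include the baseline outcome. This stands: a free baseline is the natural reading, not a stated one.

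It is also fair that a change-score contrast is valid and matches a hypothesis worded as greater improvement. Four stronger readings are tempting, and the documents do not support them:

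- **Bias or inflated type I error in the planned contrast.** There is neither. Carry-over of a chance baseline imbalance is the same extra variance seen another way, not a second harm.
- **A documented loss of a given number of women or points of power.** The figures in Step 3 rest on assumed correlations and equal variances. Nothing in the documents gives either, and no stated figure is contradicted.
- **A larger loss for self-reported minutes.** Self-report does not decide entry, but entry is cut on measured steps, so any measure correlated with steps is indirectly truncated. The documents give nothing from which to compute the loss for minutes.
- **That any common-baseline model is safe.** Step 5 shows that it is not if the covariance is a random intercept only. The free-baseline interaction does not have this weakness, because with complete data it reduces to the change score.

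**Conclusion.** The point holds as one of unused precision in an under-specified model. Both documents make baseline an outcome occasion in Aim 2a, place it before randomisation, and state neither a common baseline mean nor baseline adjustment. Read naturally, the analysis is a valid but less efficient change-score comparison.

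The size is conditional. Under equal variances, adjustment would reduce the variance by 35%, 25% or 15% at correlations of 0.3, 0.5 or 0.7. For truncated steps the reduction is about 3% to 21% under the assumed distributions, and it would be nil at a slope of 1. The argument is specific to Aim 2a, where the randomised comparison starts at the study baseline. It is worth correcting because it is cheap and settles the model before analysis; it does not threaten the validity of the aim.

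**What to change.** Add to Aim 2a in the SAP, and to the matching text in Protocol section XII:

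> The model contains time and time-by-treatment terms with no treatment main effect, so that the arms share a common baseline mean. The within-participant covariance is an unstructured 2x2 matrix. The model is fitted by likelihood to all randomised women. The unconstrained change-score contrast is reported as a sensitivity analysis.

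An acceptable alternative is to regress the 8-week value on treatment and the baseline value. The SAP should claim equivalence between the two only for complete data, because the regression omits women who lack either value while the likelihood fit keeps them. A random-intercept-only covariance should not be combined with the common-baseline model.

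The cost is a few sentences and a small change to the model code. No new data are needed. The covariance must be named, since the SAP currently names none.
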